4.6. Anti-Drug Antibody (ADA) Variables

Serum samples collected at baseline, week 16 (end of treatment) and week 36 (end of study) or ET (early termination) will be analyzed for anti-drug antibody (ADA) analysis. ADA variables include status (positive or negative) and titer as follows:

- Total number of patients whose response in the ADA assay is negative at all times
- Total number of patients whose response in the ADA assay is positive at any time point analyzed
- Pre-existing immunoreactivity - defined either as a positive ADA assay response at baseline with all post-dose ADA assay results negative, **OR** a positive assay response at baseline with all post-dose ADA assay responses less than 9-fold over baseline titer levels
- Treatment-emergent - defined as any post-treatment positive ADA assay response when the baseline is ADA negative or missing
- Treatment-boostered – defined as any post-dose positive ADA assay response that is at least 9-fold over the baseline titer level when baseline is positive in the ADA assay.
- Titer
 - Titer values
 - Titer category
 - Low (titer <1,000)
 - Moderate ($1,000 \leq \text{titer} \leq 10,000$)

- High (titer >10,000)

Neutralizing activities of ADA will be assessed for samples that are positive in the ADA assay.

4.7. Pharmacokinetic Variables

The PK variable is the serum concentration of fasinumab at scheduled time points.

5. STATISTICAL METHODS

For continuous variables, descriptive statistics will include the following: the number of patients reflected in the calculation (n), mean, standard deviation, median, first quartile (Q1), third quartile (Q3), minimum, and maximum.

For categorical or ordinal data, frequencies and percentages will be displayed for each category.

5.1. Demographics and Baseline Characteristics

Demographic and baseline characteristics will be descriptively summarized by treatment group and overall for the study based on the FAS. Parameters to be summarized include those described in [Section 4.1](#).

Continuous data will be summarized using the number of patients (n), mean, standard deviation, median, Q1, Q3, minimum, and maximum. Categorical and ordinal data will be summarized using the number and percentage of patients in each treatment group.

5.2. Medical History

Relevant medical histories at study entry will be descriptively summarized by treatment group and overall for the study based on the FAS.

All reported patient's medical history and surgical history will be presented by primary SOC, PT and treatment group. Primary SOCs will be sorted by decreasing frequency in the combined fasinumab group. Within each primary SOC, PTs will be sorted by decreasing frequency in the combined fasinumab group.

5.3. Prior/Concomitant Medications

All prior medications, dictionary coded by WHO, will be descriptively summarized by ATC class, preferred term and treatment group and overall for the study based on the safety analysis set. Summaries will present patient counts (and percentages) for all prior medications in decreasing frequency of the overall incidence of ATC followed by therapeutic class. In case of equal frequencies across anatomic or therapeutic categories, alphabetical sorting order will be used. Patients will be counted once in each ATC category (anatomic or therapeutic) linked to the medication, but may be counted several times for the same medication.

All concomitant medications, dictionary coded by WHO, will be descriptively summarized by ATC class, preferred term and treatment group, for patients in the SAF. Summaries will present patient counts (and percentages) for the concomitant medication groups described in [Section 4.3](#) for all concomitant medications, in decreasing frequency of the fasinumab group incidence of ATC followed by therapeutic class. In case of equal frequencies across anatomic or therapeutic categories, alphabetical sorting order will be used. Patients will be counted once in each ATC category (anatomic or therapeutic) linked to the medication, hence may be counted several times for the same medication.

The following will be summarized:

- Prior Medications
- Concomitant medications
- Post-treatment medications
- On-study (Concomitant + Post-Treatment) Medications

5.4. Prohibited Medications

Prohibited medications, dictionary coded by WHO, will be descriptively summarized by ATC class, preferred term and treatment group for patients in the SAF similar to the summary of concomitant medications.

5.5. Patient Disposition

The disposition of patients in the study will be summarized by treatment group and overall for all patients. The following summaries will be provided:

Summary of total screened patients, numbers of subjects in FAS, and SAF by treatment and total. Summaries of discontinuations from treatment and discontinuations from the study including reasons for discontinuation will also be presented by treatment and overall.

5.6. Extent of Study Treatment Exposure and Compliance

5.6.1. Measurement of Treatment Compliance

Compliance with protocol-defined investigational product will be calculated based on the safety set as follows:

Treatment compliance will be calculated as:

$$\frac{\text{\# of actual injections/infusions of study drug received during exposure period}}{\text{\# of planned injections/infusions of study drug during exposure period on or before the time patient discontinued from the treatment phase of the study}} \times 100\%$$

The loading dose at baseline will not be counted as a separate injection/infusion. The treatment compliance will be presented by the descriptive statistics and the number (%) of patients who have 1, 2, 3 and 4 SC injections or 1 and 2 IV infusions, respectively.

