5.3.2. Study Drug Discontinuation

Study drug may be permanently or temporarily discontinued due to medical need, as determined by the investigator.

Patients who permanently discontinue from study drug but do not withdraw from the study will be asked to return to the clinic for all remaining study visits per the visit schedule.

Patients who opt to withdraw from the study will be asked to complete study assessments, per [Section 6.2.7](#) (early termination).

Patients who discontinue from study drug early due to a potential adverse event of adjudicated arthropathy (see [Section 7.4.1.1](#)) should return to the clinic for all remaining study visits per the visit schedule.

Any patient who requires joint replacement surgery during the study will be asked to return to the site for an early termination visit ([Section 6.2.7](#)) and for the follow-up safety evaluations as described in [Section 6.3.3.9](#).

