9.5.3.4. Treatment Compliance

Treatment compliance with protocol-defined investigational product will be calculated as follows:

- Treatment compliance = (Number of actual injections of study drug during exposure period)/(Number of planned injections of study drug during exposure period on or before the time that the patient discontinues from the study) x 100%

Treatment compliance will be presented by specific ranges for each treatment group. The ranges of interest will be specified in the SAP.

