5.6.2. Exposure to Investigational product

The treatment exposure to fasinumab and placebo SC doses during the study will be presented by treatment and calculated as:

- (Date of last study drug administration – date of first study drug administration) + 28

The treatment exposure to fasinumab and placebo IV doses during the study will be presented by treatment and calculated as:

- (Date of last study drug administration – date of first study drug administration) + 56

The duration of exposure during the study will be summarized for each treatment group using the number of patients (n), mean, standard deviation, median, Q1, Q3, minimum, and maximum.

The number (%) of patients with exposure periods will be presented by specific time periods. The time periods of interest is specified as: ≥ 1 day, ≥ 8 days, ≥ 15 days, ≥ 29 days, ≥ 57 days, ≥ 85 days, and ≥ 113 days.

The duration of observation period during the study is calculated as:

- (Date of the last study visit – date of the first study drug administration) +1.

The number (%) of patients with observation periods will be presented by specific time periods. The time periods of interest is specified as: ≥ 1 day, ≥ 8 days, ≥ 15 days, ≥ 29 days, ≥ 57 days, ≥ 85 days, and ≥ 113 days.

A summary of the number of doses by treatment group will be provided.

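### The compliance denominator in SAP 5.6.1 depends on the last dose received, so final doses missed by a patient still in the treatment phase can drop out of it

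*SAP*

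**What the plan says.** The SAP 5.6.1 denominator is the number of "planned injections/infusions of study drug during exposure period on or before the time patient discontinued from the treatment phase" of the study. This sets two limits: the dose must fall in the exposure period, and it must be due no later than the patient's exit from the treatment phase. The same section states that "The loading dose at baseline will not be counted as a separate injection/infusion", and it reports how many patients had 1 to 4 SC injections and 1 or 2 IV infusions.

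SAP 5.6.2 gives SC exposure as "Date of last study drug administration – date of first study drug administration) + 28" and IV exposure as "Date of last study drug administration – date of first study drug administration) + 56". It then adds that "The number (%) of patients with exposure periods will be presented by specific time periods", so it applies the term exposure period to the durations it has just defined.

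Protocol 9.5.3.4 has the same exposure-period limit but a different second cut-off: "Number of planned injections of study drug during exposure period on or before the time that the patient discontinues from the study". Protocol 5.3.2 separates stopping drug from leaving the study: "Patients who permanently discontinue from study drug but do not withdraw from the study will be asked to return" for the remaining visits.

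**The concern.** A compliance denominator should say what the patient was due to receive. Here it is bounded by what the patient did receive, because the period closes a fixed interval after the last administration. A dose missed at the end of the course moves the close of the period earlier and can remove itself from the count.

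This pattern is foreseeable in this trial. SAP Section 1 records that dosing was stopped under the partial clinical hold before all randomized patients had finished treatment, that 563 had been randomized by then, and that patients were encouraged to stay to week 36. The percentage could then read 100% beside a dose-count table showing an incomplete course, and it could shift by a third when one dose is a day late.

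**Working it through.** The documents state no compliance figure to reproduce, so the check applies the rule to dosing patterns.

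Inputs:
- Planned SC doses: day 1 and weeks 4, 8 and 12, four in all (Protocol 5.1), which are days 1, 29, 57 and 85 (Protocol 6.1, Table 1).
- Planned IV doses: day 1 and week 8, two in all, which are days 1 and 57 (same places).
- Dose window: 7 days either side (Protocol 5.1).
- Day numbering: the first dose is day 1 and there is no day 0 (SAP 5.8).
- The day-1 loading dose counts as one dose (SAP 5.6.1).

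Formulas:
- Period length = last dose day − first dose day + 28 (SC) or + 56 (IV).
- Day-count reading: the period covers day 1 through the day equal to its length.
- Inclusive reading: the period runs through the day that is 28 or 56 days after the last dose, which is one day longer.
- Score = doses given / planned doses inside the period, for a patient still in the treatment phase.

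| Doses given | Length (days) | Score, day-count | Score, inclusive end day | Share of full schedule |
|---|---|---|---|---|
| SC day 1 | 0 + 28 = 28 | 1/1 = 100% | 1/2 = 50% | 1/4 = 25% |
| SC days 1, 29 | 28 + 28 = 56 | 2/2 = 100% | 2/3 = 67% | 2/4 = 50% |
| SC days 1, 29, 57 | 56 + 28 = 84 | 3/3 = 100% | 3/4 = 75% | 3/4 = 75% |
| SC days 1, 30 | 29 + 28 = 57 | 2/3 = 67% | 2/3 = 67% | 2/4 = 50% |
| SC days 1, 57 | 56 + 28 = 84 | 2/3 = 67% | 2/4 = 50% | 2/4 = 50% |
| SC days 1, 85 | 84 + 28 = 112 | 2/4 = 50% | 2/4 = 50% | 2/4 = 50% |
| IV day 1 | 0 + 56 = 56 | 1/1 = 100% | 1/2 = 50% | 1/2 = 50% |

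The table shows three things.

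1. Final misses are lost. On the day-count reading, a patient who takes the first SC doses on time and then misses the rest scores 100% after one, two or three doses. With SC days 1 and 29 and IV day 1, the two routes together give 3/3 against 3/6 scheduled.
2. Misses before a later dose are kept. With SC days 1 and 85 both skipped doses are in the denominator. With days 1 and 57 the skipped day 29 is counted and only the final day 85 is lost.
3. The score is unstable. The next planned dose falls exactly 28 or 56 days after an on-time one, so one day decides whether it counts. A second SC dose 1 to 7 days late, all inside the window, gives 57 to 63 days and 2/3. Given 7 days early, it gives 49 days and 2/2.

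The day-count reading is the more natural one, because a full on-time SC course comes to (85 − 1) + 28 = 112 days, or 16 weeks. The SAP does not state the end day.

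**The case against.** **The link between the two sections is inferred.** SAP 5.6.1 does not cite 5.6.2, and exposure period might mean the planned treatment period. If the period always closes soon after the last dose, the second cut-off has little left to do. Against this, 5.6.2 uses the same term for its own durations, and neither document defines it otherwise. At the least, the term is undefined and its most direct reading gives the results above.

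**Stopping drug is not always non-compliance.** A patient who has left the treatment phase is already handled by the separate cut-off, and a dose not due because of the halt or a mandated stop is not a compliance failure. This stands. It confines the problem to patients still in the treatment phase who miss final doses. How many that is depends on whether stopping drug while attending visits counts as leaving the phase, which the SAP does not say.

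**The shortfall is visible elsewhere.** Dose counts, exposure duration and treatment discontinuations with reasons are all reported (SAP 5.5 and 5.6). Compliance defines no SAP analysis set and enters no model. This also stands.

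**Stronger readings are tempting but not supported.**
- A reader might infer that any patient given half the doses scores 100%. Of the three ways to receive two SC doses including day 1, only days 1 and 29 does so, and only with the second dose not late and the day-count reading.
- A reader might expect compliance near 100% in every arm. The documents give no count of incomplete courses, and late doses would lower some scores.
- A reader might want the two day-1 SC injections counted separately. The SAP states its convention openly, and Protocol 5.1 counts four SC doses in total, so this is a preference and not an error.

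**Conclusion.** The point holds in a limited form. As written, the rule lets final missed doses leave the denominator for patients still in the treatment phase. On the day-count reading with on-time dosing, the score is 100% where the schedule-based share is 25%, 50% or 75% (SC) or 50% (IV). An inclusive end day brings the half-schedule cases to 67% (SC) and 50% (IV), and a one-day delay of the second SC dose moves 100% to 67%. These figures assume that the exposure period is the duration in SAP 5.6.2 and that the patient has not met the discontinuation cut-off.

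The effect is confined to one descriptive percentage. The week-16 comparison does not use it, and the dose counts beside it would show the shortfall. It is still worth correcting, because the percentage would contradict those counts and turns on an unstated one-day convention.

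**What to change.** - Take planned doses from the schedule: SC on day 1 and at weeks 4, 8 and 12; IV on day 1 and at week 8. Count them up to a stated date of leaving the treatment phase, independent of doses received. For a patient still in that phase, SC days 1 and 29 then scores 2/4 = 50% and IV day 1 only scores 1/2 = 50%.
- State whether stopping study drug while staying in the study counts as leaving the treatment phase. Without this, the new denominator remains ambiguous for those patients. The protocol's cut-off is leaving the study, so note the difference.
- Show compliance twice: against the full schedule, and excluding doses due after the dosing-halt date.
- Keep the convention that the loading dose counts as one dose.

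The cost is a change of SAP wording and a small derivation change. Reported compliance will be lower.

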5.6.2. Exposure to Investigational product

The treatment exposure to fasinumab and placebo SC doses during the study will be presented by treatment and calculated as:

- (Date of last study drug administration – date of first study drug administration) + 28

The treatment exposure to fasinumab and placebo IV doses during the study will be presented by treatment and calculated as:

- (Date of last study drug administration – date of first study drug administration) + 56

The duration of exposure during the study will be summarized for each treatment group using the number of patients (n), mean, standard deviation, median, Q1, Q3, minimum, and maximum.

The number (%) of patients with exposure periods will be presented by specific time periods. The time periods of interest is specified as: ≥ 1 day, ≥ 8 days, ≥ 15 days, ≥ 29 days, ≥ 57 days, ≥ 85 days, and ≥ 113 days.

The duration of observation period during the study is calculated as:

- (Date of the last study visit – date of the first study drug administration) +1.

The number (%) of patients with observation periods will be presented by specific time periods. The time periods of interest is specified as: ≥ 1 day, ≥ 8 days, ≥ 15 days, ≥ 29 days, ≥ 57 days, ≥ 85 days, and ≥ 113 days.

A summary of the number of doses by treatment group will be provided.

5.7. Analyses of Efficacy Variables

5.7.1. Analysis of Primary Efficacy Variable(s)

The primary endpoint in the study is the change from baseline to week 16 in the average daily LBPI NRS score. The following hypotheses will be tested (with no control for multiplicity):

- H₁: No difference in the change from baseline to week 16 in the average LBPI NRS score for fasinumab 6mg SC Q4W and Placebo.
- H₂: No difference in the change from baseline to week 16 in the average LBPI NRS score for fasinumab 9mg SC Q4W and Placebo.
- H₃: No difference in the change from baseline to week 16 in the average LBPI NRS score for fasinumab 9mg IV Q8W and Placebo.

Statistical Model

The primary efficacy variable, change from baseline in LBPI score, will be analyzed using a mixed-effect model repeated measures (MMRM) approach based on the mITT. The model will include the randomization strata, baseline LBPI score, treatment, study week, and treatment-by-week interaction. Denominator degrees of freedom will be estimated using Kenward-Roger's approximation. Data from all patients, including data collected after discontinuing treatment up to the earlier of withdrawal of consent, week 16 or 5 weeks after the last dose of study drug, will be used in the primary efficacy analyses according to the intent-to-treat principle using the MMRM approach with no imputation for missing data.

The fitting of MMRM will be performed using MIXED procedure in SAS with an unstructured covariance matrix to model the within-patient errors. If the model does not converge using unstructured covariance matrix, a simpler covariance structure with fewer parameters will be

used according to the following order: heterogeneous autoregressive (1)ARH(1), Compound symmetry (CSH), Toeplitz (TOEP).

The Least-Squares means estimates for the mean change from baseline to week 16, as well as the differences of the estimates between fasinumab doses and placebo, with their corresponding standard errors, p-values and associated 95% confidence intervals will be provided from the MMRM model. The graph of LS-mean +/- SE by visit will be provided. In addition, the absolute value at week 16 and change from baseline to week 16 in LBPI NRS score will be summarized and graphed by visit.

Sample SAS codes that can be used to implement the MMRM analysis are shown below:

```
proc mixed data=LBPI_NRS;  
  class subid trt week stratum1 stratum2 stratum3;  
  model chg = baseline trt stratum1 stratum2 stratum3 week trt*week  
  /ddfm = kr;  
  repeated week / type=un subject=subid;  
  lsmeans trt*week/ slice=week pdiff cl;  
run;
```

Where stratum1, stratum2, and stratum3 are baseline LBPI NRS score (<7 , ≥ 7), duration of chronic back pain (<5 years, ≥ 5 years), and maximum K-L category (≤ 2 , >2).

Sensitivity analysis:

Sensitivity analyses will be performed the same way for the primary and secondary variables (RMDQ total score and PGA) using the FAS.

Subgroup analysis:

Descriptive analyses will be performed on the primary endpoint and the secondary endpoints (RMDQ total score and PGA) to summarize the treatment effects across subpopulations defined by baseline randomization strata (baseline LBPI NRS score, duration of chronic back pain, and maximum K-L score category), demographics (age group, sex, race) and baseline characteristics (weight and BMI categories). Subgroup analysis by osteoarthritis (OA) subgroup will be performed. OA subgroup is defined as:

1. Medical History of OA
2. Kellgren Lawrence Grade $\geq \geq 2$ radiographic evidence of hip or Grade $\geq \geq 3$ radiographic evidence of knee
3. Either (1) or (2)

Subgroup analysis based on other medical conditions may also be performed.

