Assuming a significance level of 0.05 and [REDACTED], an enrollment of 200 patients per treatment group will provide at least 91% power to detect a treatment difference [REDACTED] between fasinumab 9 mg SC Q4W and placebo for the mean change from baseline to week 16 in the average daily LBPI NRS score [REDACTED]. The assumed treatment difference and common SD were estimated based on results from a phase 2b multiple dose study of tanezumab (5, 10, and 20 mg IV Q8W) versus placebo and naproxen (500 mg BID) in patients with chronic LBP. The LS mean change (standard error [SE]) from baseline to week 16 of -2.18 (0.14) and -1.25 (0.16) for tanezumab 20 mg (n = 295) and placebo (n = 230) were used to estimate the treatment difference and common SD.

A combination of Hochberg method and gatekeeping method will be used for multiplicity adjustment to maintain the study-wise type I error rate at the 0.05 level. For analysis secondary endpoints that are continuous variables, the analysis method is the same as for the primary variable but without multiplicity adjustment. For analysis of categorical variables in secondary endpoints, the Cochran-Mantel-Haenszel approach stratified by the randomization strata will be used.

The safety analyses will be based on reported TEAEs, adverse events of special interest (AESI), and other safety information (clinical laboratory evaluations, vital signs, and 12-lead ECG).

TABLE OF CONTENTS

AMENDMENT HISTORY	2
CLINICAL STUDY PROTOCOL SYNOPSIS.....	5
LIST OF ABBREVIATIONS AND DEFINITIONS OF TERMS.....	14
1. INTRODUCTION AND RATIONALE.....	16
1.1. Introduction.....	16
1.2. Rationale	18
1.2.1. Rationale for Study Design.....	18
1.2.2. Rationale for Dose Selection	18
2. STUDY OBJECTIVES	19
2.1. Primary Objective.....	19
2.2. Secondary Objectives	19
2.3. Safety Objectives	19
2.4. Other Objectives	19
3. STUDY DESIGN	20
3.1. Study Description and Duration	20
3.1.1. Study Stopping Rules	22
3.2. Planned Interim Analysis.....	22
3.3. Study Committees.....	23
3.3.1. Independent Data Monitoring Committee.....	23
3.3.2. Adjudication of Arthropathy Events.....	23
4. SELECTION, WITHDRAWAL, AND REPLACEMENT OF PATIENTS.....	23
4.1. Number of Patients Planned	23
4.2. Study Population.....	23
4.2.1. Inclusion Criteria	23
4.2.2. Exclusion Criteria	24
4.3. Premature Withdrawal from the Study.....	27
4.4. Replacement of Patients	27
5. STUDY TREATMENTS.....	28
5.1. Investigational Treatment	28
5.2. Rescue Treatment	28
5.2.1. Paracetamol/Acetaminophen	28

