9. STATISTICAL PLAN

This section provides the basis for the statistical analysis plan (SAP) for the study. The SAP may be revised during the study to accommodate amendments to the clinical study protocol and to make changes to adapt to unexpected issues in study execution and data that may affect the planned analyses. The final SAP will be issued before the database is locked.

Analysis variables are listed in [Section 8](#).

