9.1. Statistical Hypothesis

The primary endpoint in the study is the change from baseline at week 16 in the average daily LBPI NRS score. The following hypotheses will be tested:

H1i: fasinumab group #i versus placebo, where i=1, 2, 3.

Group #1 = fasinumab 6 mg SC Q4W and placebo IV Q8W

Group #2 = fasinumab 9 mg SC Q4W and placebo IV Q8W

Group #3 = fasinumab 9 mg IV Q8W and placebo SC Q4W

Placebo = placebo SC Q4W and placebo IV Q8W

A combination of Hochberg method and gatekeeping method will be used for multiplicity adjustment of the 3 hypotheses above. Hochberg method will be applied for hypotheses H_{11} (fasinumab 6mg SC Q4W versus placebo) and H_{12} (fasinumab 9 mg SC Q4W versus placebo) at a 2-sided alpha level of 0.05. The larger of the 2 p-values from the analysis for H_{11} and H_{12} will be compared with 0.05. If the larger p-value is less than or equal to 0.05, both H_{11} and H_{12} will be rejected and fasinumab 6 mg SC and 9 mg SC will be declared statistically significantly better than placebo. If the larger p-value is greater than 0.05, the smaller p-value of the 2 p-values from the analysis for H_{11} and H_{12} will be compared with 0.025. If the smaller p-value is less than or equal to 0.025, the corresponding hypothesis will be rejected and the treatment group declared statistically significantly better than placebo.

If both H_{11} and H_{12} are positive, then H_{13} (fasinumab 9 mg IV Q8W) will be tested at a 2-sided alpha level of 0.05.

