9.5.2.2. Secondary Efficacy Analysis

Tests will be performed at the 2-sided, 5% significance level without multiplicity adjustment. For analysis of continuous variables in secondary endpoints, the analysis method is the same as for the primary variables. For analysis of categorical variables in secondary endpoints, the Cochran-Mantel-Haenszel approach stratified by the randomization strata will be used.

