The U.S. Food and Drug Administration (FDA) placed the study on partial clinical hold before enrollment was completed and dosing was prematurely terminated before all randomized patients had completed treatment. The study was enrolling patients with chronic low back pain, some of whom had advanced osteoarthritis, to doses that exceeded those being pursued in the concurrent or planned osteoarthritis studies which limits dosing to 6 mg SC Q8W. Since an event of adjudicated arthropathy was observed in the CLBP study in a patient with advanced OA using a dose higher than that being evaluated in the ongoing OA study, the FDA requested that the study be placed on hold until the protocol could be amended to either remove patients with OA or reduce the doses. A decision was made not to amend the protocol to enable dosing to be resumed. At the time of the clinical hold, 563 patients had been randomized into the study. Patients will be encouraged to remain in the study and be followed for all study visits until completion of the week 36 visit to continue to monitor safety and to allow complete data collection.

The planned analyses take this change into account.

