2.2. Sample Size and Power Considerations

Approximately 800 patients (200 patients per treatment) will be randomized into 4 treatment groups. Assuming a significance level of 0.05 [REDACTED], an enrollment of 200 patients per treatment group will provide at least 91% power to detect a treatment difference [REDACTED] between fasinumab 9 mg SC Q4W and placebo for the mean change from baseline to week 16 in the average daily LBPI NRS score [REDACTED]. The assumed treatment difference and common SD were estimated based on results from a phase 2b multiple dose study of tanezumab (5, 10, and 20 mg IV Q8W) versus placebo and naproxen (500 mg BID) in patients with chronic LBP (Kivitz 2013). The Least Squares (LS) mean change (SE) from baseline to week 16 of -2.18 (0.14) and -1.25 (0.16) for tanezumab 20 mg (n = 295) and placebo (n = 230) were used to estimate the treatment difference and common SD.

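### SAP 5.7.1 drops the protocol's multiplicity control for the three primary comparisons, gives no reason specific to multiplicity, and does not say whether the p-values are nominal

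*SAP*

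**What the plan says.** **Protocol.** Section 9.1 states: "A combination of Hochberg method and gatekeeping method will be used for multiplicity adjustment of the 3 hypotheses above". The larger of the two SC p-values is compared with 0.05. If it fails, the smaller is compared with 0.025. The 9 mg IV dose is tested at two-sided 0.05 only when both SC doses have succeeded. The synopsis gives the purpose: the combined procedure "will be used for multiplicity adjustment to maintain the study-wise type I error rate at the 0.05 level". Unadjusted testing is reserved for the secondary endpoints; section 9.5.2.2 says "Tests will be performed at the 2-sided, 5% significance level without multiplicity adjustment".

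**SAP.** Section 5.7.1 lists the same three comparisons under the words "The following hypotheses will be tested (with no control for multiplicity". It then promises p-values and 95% confidence intervals from the repeated-measures model.

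**Context.** SAP section 1 reports a partial clinical hold after 563 patients had been randomized, and that "dosing was prematurely terminated before all randomized patients had completed treatment". It adds "The planned analyses take this change into account" without mentioning multiplicity. SAP 2.2 still carries the 0.05 level and says that "an enrollment of 200 patients per treatment group will provide at least 91% power to detect a treatment difference". SAP 1.1.5, whose heading promises modifications from the protocol's statistical section, names only the protocol version on which the SAP is based. SAP 1.1.6 records no revisions. SAP 7 reports, in the past tense, two unblinded interim analyses of efficacy.

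**The concern.** The protocol says when a primary hypothesis counts as rejected. The SAP removes that rule and puts nothing in its place. A reader who sees p = 0.04 for one dose cannot tell whether it is a positive result or a nominal figure.

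If it is taken as a positive result, two things follow. The study-wise 0.05 guarantee is lost. The IV dose could also be claimed when one or both SC doses have failed, which the protocol's gate excludes.

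Timing adds to the need for a record. The available SAP text was written after two unblinded efficacy analyses, and the documents do not say when or why the control was removed. Nothing in them shows a data-driven change: independent personnel ran the interims, and the study medical monitor and biostatistician are said to remain blinded at the subject level. A rule left open until after database lock, however, could only be chosen post hoc.

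**Working it through.** **Inputs**
- Allocation 1:1:1:1 with one shared placebo arm (protocol 3.1), so the three test statistics have pairwise correlation 0.5.
- Protocol rule: section 9.1, as described above.
- SAP rule: each test read at two-sided 0.05. SAP 5.7.1 does not state this level. It is inferred from the 95% intervals, SAP 2.2, and the two-sided 5% level in protocol 9.5.2.2 for unadjusted secondary tests.
- Effect and SD for power, from the tanezumab phase 2b figures in SAP 2.2: difference 2.18 − 1.25 = 0.93; SDs 0.14 × √295 = 2.405 and 0.16 × √230 = 2.427, pooled 2.414.
- Patients per arm after the hold: 563 / 4 = 140.75, assuming balance.

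**Step 1. The protocol's 0.05.** Simulating three statistics that share a placebo arm (2 to 4 million trials per scenario), the Hochberg-plus-gate rule gives a 4.8% chance of any false rejection when no dose works. It reaches 5.0% when only 9 mg SC is extremely effective, or when both SC doses are and the IV dose is null. The stated 0.05 is reproduced as the bound.

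**Step 2. The SAP rule when no dose works.** Conditioning on the placebo mean x, with 1.96 × √2 = 2.772:

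P(at least one rejection) = 1 − ∫ φ(x) [Φ(x + 2.772) − Φ(x − 2.772)]³ dx = 0.1254.

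Simulation agrees. Independent tests would give 1 − 0.95³ = 0.143, and the upper bound is 3 × 0.05 = 0.15.

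**Step 3. Other configurations** (effective arm at 0.93, about 141 per arm)

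| Situation | SAP as written | Protocol 9.1 |
|---|---|---|
| No dose works: any false rejection | 12.5% | 4.8% |
| No dose works: false rejection favouring fasinumab | 6.3% | 2.4% |
| One SC dose works: any false rejection | 9.1% | 4.5% |
| One SC dose works: favouring fasinumab | 4.5% | 2.5% |
| Only IV works: any false rejection | 9.1% | 4.8% |
| Only IV works: favouring fasinumab | 4.5% | 2.4% |
| No dose works: IV p ≤ 0.05 without both SC doses at p ≤ 0.05 | 4.7% | 0 |

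The last row can be checked by hand. IV alone reaches p ≤ 0.05 in 5.0% of trials and all three doses do so in 0.3%, and 5.0 − 0.3 = 4.7.

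**Step 4. What restoring control costs.** Single-test power is Φ(0.93 / (2.414 × √(2/n)) − z), with z = 1.960 at 0.05 and 2.241 at 0.025. At n = 140.75 the first term is 3.232. Power is then Φ(1.272) = 90% at 0.05 and Φ(0.990) = 84% at 0.025. With 20% lacking week-16 data (n = 112.6) it is 82% and 74%. If all three doses work equally and no data are lost, simulated power is 89% rather than 90% for each SC dose, and 78% rather than 90% for IV. If only IV works, it is claimed in 0.6% of trials under the gate.

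**Step 5. Can the hold explain the change by itself?** A smaller sample lowers power. It does not alter the type I error of three unadjusted tests, so early stopping alone gives no reason to drop the control.

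**The case against.** The best defence is that the change is disclosed in plain words and that its natural reading is nominal p-values. SAP 5.7.1 omits the protocol's language about declaring a dose superior. The hold ended dosing early, and protocol section 9 lets the SAP be revised "to make changes to adapt to unexpected issues in study execution and data that may affect the planned analyses". Protocol 9.7 also allows reduced reporting after premature termination. SAP 2.2 looks like design text carried over from the protocol, since it still speaks of 800 patients, and is weak evidence of confirmatory intent. On this view the 12.5% never arises and only a documentation gap remains.

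Part of this stands. A non-confirmatory analysis is a reasonable response to the hold, the SAP may be changed, and the inflation depends on reading p ≤ 0.05 as a claim. The power figures are also rough. The primary analysis uses data only up to 5 weeks after the last dose, so a patient last dosed at week 8 contributes nothing at week 16, and loss could exceed 20%.

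The rest does not remove the problem. Permission to change is neither a reason nor a replacement rule. The SAP labels its subgroup analyses descriptive but says that the primary hypotheses will be tested. Silence in SAP 1.1.5 cannot mean that nothing changed: the primary analysis set also moved from the full analysis set (protocol 9.3.1) to the modified intent-to-treat set (SAP 5.7.1) without being listed there.

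**Conclusion.** The concern holds. The protocol and SAP disagree on how the primary hypotheses are decided, and the SAP neither gives a reason specific to multiplicity nor states the status of its p-values. Read as claims, the SAP's tests raise the chance of a false primary rejection from 4.8% to 12.5% when no dose works, and from 4.5–4.8% to 9.1% when one dose works. These figures assume equal arms, normal test statistics and two-sided 0.05 per test. If the p-values are meant as nominal, the inflation does not apply, but the SAP has to say so. Because this is the decision rule for the primary endpoint, it must be settled before database lock.

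**What to change.** Choose one route before database lock and write it into SAP 5.7.1.

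- **(a) Claims of significance are intended.** Restore protocol 9.1: Hochberg on the two SC doses at two-sided 0.05, and the IV dose at 0.05 only if both are rejected. Report the unadjusted p-values and 95% intervals as nominal. The wording is simple but the route costs power, as Step 4 shows. If only the IV dose works it can almost never be claimed, which follows from the protocol's own gate.
- **(b) No confirmatory claim is intended after the hold.** State that no hypothesis will be declared significant and that all p-values are nominal. This costs no power but gives up any claim of significance.

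Under either route, use SAP 1.1.5 to say how 5.7.1 relates to protocol 9.1, with the reason for any departure and its date relative to the two unblinded interim analyses. The change of primary analysis set belongs in the same list, since restoring Hochberg alone would not restore the protocol's primary test. Model estimates, standard errors and unadjusted p-values are the same under both routes, so no reprogramming of the model is needed.
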